4. STUDY DESIGN

4.1. Overall Design

The original design was a randomized study to evaluate the risk of MACE for relugolix compared with leuprolide acetate. The study was intended to collect clinical and cardiovascular risk factor data on patients ages 18 and older who were receiving relugolix or leuprolide acetate for their prostate cancer or as adjunct to radiation therapy with a treatment plan to be on at least 12 months of continuous ADT. Amendment 1 of the protocol is provided for reference ([Appendix 5](#)).

This study was discontinued by the Sponsor on 01 Dec 2023, in an effort to mitigate any treatment interruptions, actively enrolled patients will be allowed to remain on study drug up to a period of 12 months ending Dec 2024. During this discontinuation phase, all active investigative sites will be expected to formulate a transition plan for their study patients from this clinical study to SOC as soon as practicable. This protocol has been modified to account for the shift to a discontinuation phase study.

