4.4. End of Study Definition

The end of study is defined as the date of the last dispensation (last injection of leuprolide; last delivery of relugolix) before the patient transitions to SOC treatment.

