7.4. Patient and Study Completion

For an individual patient, study completion is defined as their last study communication at the end of the study (including any follow-up visits or telephone contact for determination of resolution of an adverse event).

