2. STUDY DESIGN

2.1. Summary of Study Design

The original study was a randomized open-label study to evaluate the risk of MACE in patients with prostate cancer with defined high-risk cardiovascular disease who are appropriate to be treated either with relugolix or leuprolide acetate for a planned duration of 12 months or more. This study was terminated by the Sponsor on 01 Dec 2023. In an effort to avoid treatment interruptions, patients who had been enrolled will be allowed to remain on study drug up to a period of 12 months ending Dec 2024 if they choose to remain in the discontinuation phase of the study. During this discontinuation phase, all active investigative sites will be expected to formulate a transition plan for their study patients from this clinical study to standard of care (SoC) as soon as practicable.

The study population includes men ages 18 and older with prostate cancer. Deviations from inclusion and exclusion criteria are not allowed. Eligibility criteria are described below.

Inclusion Criteria:

1. Was previously enrolled in the original version and amendment 1 of this study
2. Has voluntarily resigned and dated the informed consent form prior to transition to the discontinuation phase of this study

[figure not shown]
Exclusion Criteria:

Not applicable as patients were previously excluded under the original version and amendment 1.

Disclosure Statement:

This is a randomized study with collection of clinical data at baseline and at follow-up.

Figure 1: Study Schema

Abbreviations: ADT = androgen deprivation therapy; ER = emergency room; MACE = major adverse cardiovascular event; PSA = prostate-specific antigen; R = randomization.

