4. GENERAL CONSIDERATIONS FOR DATA ANALYSES AND HANDLING OF MISSING DATA

4.1. Data Presentation Conventions

All statistical analyses will be conducted using SAS® Version 9.4 or higher.

Statistical tests for the primary and secondary endpoints will be assessed at a two-sided $\alpha = 0.05$ significance level, and all confidence intervals will be reported as two-sided, unless otherwise stated.

Where appropriate, variables will be summarized descriptively by study visit. For the categorical variables, the count and proportions of each possible value will be tabulated by treatment group. For continuous variables, the number of patients with non-missing values, mean, median, standard deviation (SD), minimum, and maximum values will be tabulated.

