5. STUDY DRUG EXPOSURE AND COMPLIANCE

Following randomization, patients will follow SOC practices with their investigator, which for the leuprolide acetate group will include visits for injection of leuprolide acetate. The investigator must record all dates of leuprolide acetate administration in the electronic data capture system. For the relugolix group, patients will self-administer relugolix at home.

Each patient will have a follow-up visit (either in office or by telehealth; per the investigator's discretion) during this discontinuation phase until they transition to SOC.

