6.1. Adverse Events and Serious Adverse Events

Per protocol, serious adverse events will be reported by the patient (or, when appropriate, by a caregiver, surrogate, or the patient's legally authorized representative) using questionnaires submitted electronically. Serious adverse events will also be reported by the investigators electronically through the electronic data capture.

The severity of all treatment-emergent adverse events will be evaluated by the investigator based on the National Cancer Institute's Common Terminology Criteria for Adverse Events (NCI CTCAE v5.0) and will be coded to preferred term and system organ class using the Medical Dictionary for Regulatory Activities 25.1 or higher.

Treatment-emergent serious adverse event is defined as any serious adverse event that occur after administration of the first dose of study drug and prior to the end of the study.

Serious adverse event summaries will be based on treatment-emergent adverse events, unless otherwise specified. Listing for all serious adverse events will be provided.

Tabular summaries with the number and percentage of patients with the following adverse events (but not limited to) will be provided:

- Overview of adverse events
- All adverse events
 - By system organ class and preferred term
 - By decreasing frequency of preferred term
 - By decreasing frequency of preferred term and relatedness to study drug

- All serious adverse events
 - By system organ class and preferred term
 - By decreasing frequency of preferred term
- Serious adverse events leading to study drug withdrawn
 - By system organ class and preferred term
 - By decreasing frequency of preferred term
- Serious adverse events in fatal outcome
 - By system organ class and preferred term
 - By decreasing frequency of preferred term

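### AE tables give only crude percentages by arm and no observation time, while the treatment-emergent window can close at arm-specific dates

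*SAP*

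**What the plan says.** SAP 6.1 sets the adverse event output: "Tabular summaries with the number and percentage of patients with the following adverse events (but not limited to) will be provided". No rate, person-time or time-to-event summary is named. Under SAP 4.1, for categorical variables "the count and proportions of each possible value will be tabulated by treatment group", so the two arms stand side by side.

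SAP 5 carries the title of exposure and compliance, but it opens "Following randomization, patients will follow SOC practices with their investigator" and goes on to describe conduct only. SAP 4.3.3 defines treatment duration, with imputation rules, but no summary in the SAP uses it.

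A treatment-emergent SAE is "any serious adverse event that occur after administration of the first dose of study drug and prior to the end of the study". The SAP does not define that end. The protocol offers two candidates:

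- Section 4.4: "The end of study is defined as the date of the last dispensation (last injection of leuprolide; last delivery of relugolix", in each case before the patient's move to standard of care.
- Section 7.4: for the individual patient, "study completion is defined as their last study communication at the end of the study".

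On follow-up, SAP 2.1 says that enrolled patients "will be allowed to remain on study drug up to a period of 12 months ending Dec 2024". Protocol 4.1 asks sites to "formulate a transition plan for their study patients from this clinical study to SOC as soon as practicable". Protocol 8.2.1 expects no questionnaires after that move.

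**The concern.** A crude percentage mixes the risk of an event with the length of time a patient was watched. Observation time here varies for three reasons: entry was staggered, enrolment stopped in December 2023, and each patient leaves for standard of care at a time settled locally. With no observation-time table, a reader cannot tell a low risk from a short follow-up.

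The documents also contain one route by which the arms could differ systematically. If SAP 6.1 means the protocol 4.4 date, the window closes at a last injection that may cover 3 or 6 months, or at a last delivery of tablets whose interval may be shorter. SAEs after that date drop out of the treatment-emergent tables, and the length of the lost period depends on the formulation. Safety is the only objective left, and protocol 9.3 assigns the detail of the adverse event analysis to the SAP, so the gap belongs there.

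**Working it through.** **The plan's own figure.** The documents state no AE percentage or follow-up time to reproduce. The nearest figure is the original target of 237 events (SAP 2.2: hazard ratio 0.65, 90% power, two-sided 0.05, one look at 60%). The Schoenfeld formula gives 227 and Freedman 234. Schoenfeld with O'Brien-Fleming-type spending for efficacy gives 228.3, and adding non-binding futility of the same type (assumed) gives 236.4, that is 237. The figure is consistent, and nothing below depends on it.

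**Inputs from the documents.** Leuprolide is given as a 3-M or 6-M depot (protocol 6.1). Relugolix comes in 45-tablet bottles (protocol 6.2). The discontinuation phase lasts up to 12 months in both arms. Allocation is 1:1. The one-year MACE rate of 6.5% for leuprolide (SAP 2.2) serves as one illustrative risk.

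**Assumptions.** A second annual risk of 20%; a constant and equal hazard in both arms; a full 12-month phase; relugolix deliveries every 45 or 90 days (the interval is not stated).

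**Last dispensation within 12 months.** 6-M depot: month 6. 3-M depot: month 9. Relugolix: month 10.5 with 45-day deliveries, month 9 with 90-day deliveries.

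**Formula.** h = -ln(1 - annual risk); crude percentage = 1 - exp(-h × months/12). At 20%, h = 0.2231, so month 6 gives 1 - exp(-0.1116) = 10.6%, month 9 gives 15.4% and month 10.5 gives 17.7%.

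| Leuprolide v relugolix window | 6.5% annual risk | 20% annual risk |
|---|---|---|
| 6-M v 45-day | 3.3% v 5.7% (ratio 1.73) | 10.6% v 17.7% (1.68) |
| 3-M v 45-day | 4.9% v 5.7% (1.16) | 15.4% v 17.7% (1.15) |
| 6-M v 90-day | 3.3% v 4.9% (1.49) | 10.6% v 15.4% (1.46) |
| 3-M v 90-day | 4.9% v 4.9% (1.00) | 15.4% v 15.4% (1.00) |

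Ratios are taken before rounding. A leuprolide arm that mixes depots falls between its two rows. Where the arms differ, relugolix looks worse.

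**Adding time before the stop.** Assume entry uniform over 0 to 24 months before the stop, at 20% annual risk. The mean proportion event-free at the stop is (1 - 0.64)/(2 × 0.2231) = 0.807, so 19.3% in each arm have had an event by then. Multiplying 0.807 by the event-free proportion in the later window gives 27.9% (6-M) or 31.8% (3-M) against 33.6% (relugolix, 45-day), ratios 1.21 and 1.06.

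**With person-time as denominator.** Counting time from first dose to the end of the window, both arms show the same rate: 6.7 per 100 patient-years at 6.5%, 22.3 at 20%.

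**Why SAP 4.3.3 duration cannot be that denominator.** It runs from first to last dose and so omits the cover of the final depot. With 12 months of cover and 20 events per 100 patients in every group, it yields 20/50 = 40 per 100 patient-years for the 6-M depot, 20/75 = 27 for the 3-M depot and 20/100 = 20 for daily relugolix.

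**The case against.** Much can be said against a stronger reading.

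- A reader might infer that the early termination itself distorts the comparison. It does not. With 1:1 randomisation both arms have the same expected entry pattern, so a common calendar stop gives the same expected percentage at equal risk (19.3% in each arm above). It makes the percentages hard to read as risks, not unequal.
- A reader might infer that the arms move to standard of care at different times. The documents give one rule for both. Unequal moves are possible in an open-label trial: mean observation of 12 against 9 months at an equal 20 events per 100 patient-years would show as 18.1% against 13.9%. But that gap is pure assumption.
- A reader might infer that a between-arm AE analysis is at stake. The objective is to describe the safety of relugolix, and no AE test or between-arm estimate is planned.
- The protocol 4.4 effect disappears if the SAP means the last study communication.
- Part of the need is met already: the list of tables is expressly left open, every SAE is listed, and disposition is summarised.
- Rates can mislead too. Protocol 2.1 describes an early rise in cardiovascular risk with GnRH agonists. If 10% of each arm had an event in month 1 and none later (assumed), with 12 against 9 months of observation, the crude table would rightly show 10% in both, while the rates would be about 11 and 15 per 100 patient-years. Departure related to health would bias rates as well.

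The first four points limit the concern and are accepted. The fifth does not remove it: leave to add tables is not a specification, and even a single-arm percentage needs its observation time. The sixth shapes the remedy.

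**Conclusion.** The concern holds in limited form. The SAP specifies only crude AE percentages by arm and no summary of observation or exposure, although observation time varies between patients. It also leaves open which end-of-study date closes the treatment-emergent window. If that is the protocol 4.4 date, equal risks can appear as unequal percentages, with ratios of about 1.0 to 1.7 over a 12-month discontinuation phase, or 1.21 (6-M) and 1.06 (3-M) once staggered entry is added at 20% annual risk with 45-day deliveries. If it is the protocol 7.4 date, this source of imbalance is absent, and what remains is that the percentages cannot be read without follow-up time. The sizes rest on assumed risks, delivery intervals, entry pattern and a constant hazard. The documents do not show that the arms will in fact be observed for different lengths of time.

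**What to change.** 1. In SAP 6.1, state one end date for the AE window, defined the same way in both arms, and reconcile it with protocol 4.4 and 7.4.
2. In SAP 5, add a table by arm of observation time (first dose to the end of that window) and total patient-years. Do not use the SAP 4.3.3 treatment duration as observation time.
3. For SAEs, fatal SAEs and AEs leading to discontinuation, report beside the percentages the number of patients with a first event per 100 patient-years at risk, with an exact Poisson 95% confidence interval by arm. Add cumulative incidence at fixed times, such as 6 and 12 months, because the rate assumes a roughly constant hazard.

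The cost is SAP wording and a few more table columns; the plan already provides for first-dose dates and event onset dates. The downside is that rates can mislead when events cluster early, so the percentages should stay. The tables remain descriptive.

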Despite the literature evidence available in the last years from different type of studies (randomized controlled, observational, and meta-analyses), GnRH receptor agonists remain the standard of care for men requiring androgen deprivation therapy (ADT) for advanced prostate cancer. Furthermore, although guidelines on use of ADT in prostate cancer do highlight the need for screening and intervention to prevent/treat diabetes and cardiovascular disease, there is no recommendation for any particular type or class of ADT ([Schaeffer et al. 2021](#)). Currently GnRH receptor agonists are the standard of care. One major disadvantage of using an agonist to suppress testosterone is the initial stimulation of the hypothalamus-pituitary-gonadal axis that occurs prior to desensitization and lasts 1 to 3 weeks. This results in a rise in luteinizing hormone and follicle stimulating hormone, a subsequent testosterone surge, and in some men, an increase in clinical symptoms ([Oh et al. 2010](#)), including increased bone pain, spinal cord compression, pathologic fracture, bladder outlet obstruction, and even death ([Oh et al. 2010](#)). Cardiovascular events also have emerged as an immediate post-treatment concern with GnRH agonists, perhaps due to the hormone surge ([Margel et al. 2019](#); [Shore 2020](#)).

Since 2010, the Food and Drug Administration (FDA) has required that the risk of cardiovascular disease be included in the safety information for GnRH receptor agonists. Eligard® and Lupron Depot® labeling include a warning of an increased risk of myocardial

infarction, sudden cardiac death, and stroke associated with use of GnRH receptor agonists in men and recommend that patients be monitored for symptoms and signs suggestive of development of cardiovascular disease (Eligard USPI 2019; Lupron Prescribing Information 2019). The increased risk associated with the use of GnRH receptor agonists is hypothesized to occur in two distinct timeframes. An early increase in cardiovascular risk has been described in men with preexisting cardiovascular disease, possibly from plaque rupture and resultant thrombosis, whereas a later increase in risk may occur from the resulting hypogonadal state with an increase in central obesity, insulin resistance, hypertension, and hyperlipidemia (Albertsen et al. 2014; Crawford et al. 2017; Margel et al. 2019).

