8.3. Adverse Events and Serious Adverse Events

Adverse events and serious adverse events will be reported by the patient (or, when appropriate, by a caregiver, surrogate, or the patient's legally authorized representative) using the questionnaires. The CRO is responsible for checking the questionnaires for selective safety data

(ie, serious adverse events and nonserious adverse events leading to treatment discontinuation) and for recording, reporting, and following up of these events.

Selective safety data will also be reported by the investigator.

All serious adverse event reporting is conducted in accordance with the Code of Federal Regulations Title 21 312.32.

8.3.1. Time Period and Frequency for Collecting Adverse Event and Serious Adverse Event Information

All adverse events and serious adverse events reported in the follow-up questionnaires will be collected from the signing of the ICF until the final study visit at the time points specified in the SoA (Section 1.3), irrespective of a causal relationship.

For serious adverse events and nonserious adverse events leading to treatment discontinuation reported in the follow-up questionnaires, the CRO is responsible to ensure these selective safety data are recorded and reported to the sponsor (or designee) within 5 calendar days of receipt unless there are suspected unexpected fatal or life-threatening serious adverse reaction reports, in which case they will be reported to the sponsor or designee within 2 business/3 calendar days, whichever is shorter, as indicated in [Appendix 2](#). The CRO will also submit any updated selective safety data to the sponsor as indicated in [Appendix 2](#).

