- Patients must be informed that their participation is voluntary. Patients will be required to sign a statement of informed consent that meets the requirements of 21 CFR 50, local regulations, ICH guidelines, Health Insurance Portability and Accountability Act requirements, where applicable, and the IRB/IEC or study center.
- Patients can sign a paper ICF to be eligible for the discontinuation phase of the study. Electronic informed consent (eConsent) will not be available.
- The medical record must include a statement that written informed consent was obtained to allow the patient to continue in the discontinuation phase and the date the written consent was obtained. The authorized person obtaining the informed consent must also sign the ICF.
- Patients must be re-consented to the most current version of the ICF(s) during their participation in the study. Re-consent must occur through the paper ICF consent.
- A copy of the paper ICF(s) must be provided to the patient and the patient's legally authorized representative and the investigator will maintain the signed original document within the patient's record file per local requirements.
- For patients who consented to prior versions of the protocol via eConsent, a copy of the electronic ICF(s) will be available to the patient to review and print a copy via the secure portal.
- The investigator will also fully document the informed consent process in the patient's source records.
- Due to the study entering into a discontinuation phase, all enrolled patients will need to be reconsented.

Data Protection

- Patients will be assigned a unique identifier by the sponsor. Any patient records or datasets that are transferred to the sponsor will contain the identifier only; patient names or any information which would make the patient identifiable will not be transferred.
- The patient must be informed that his personal study-related data will be used by the sponsor in accordance with local data protection law. The level of disclosure must also be explained to the patient who will be required to give consent for their data to be used as described in the informed consent
- The patient must be informed that his medical records may be examined by Clinical Quality Assurance auditors or other authorized personnel appointed by the sponsor, by appropriate IRB/IEC members, and by inspectors from regulatory authorities.

Dissemination of Clinical Study Data

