1. INTRODUCTION

This document describes detailed statistical analysis to be conducted for study protocol amendment 2 MVT-601-056 (dated 29 Feb 2024), entitled, “Relugolix Versus Leuprolide in Patients with Prostate Cancer: A Randomized Open-Label Study to Assess Major Adverse Cardiovascular Events (REPLACE-CV).” This Statistical Analysis Plan (SAP) will provide details to further elaborate statistical methods as outlined in the protocol amendment 2 MVT-601-056 as well as analysis conventions to guide the statistical programming work.

This SAP is developed in accordance with the International Council on Harmonisation (ICH) guidelines:

- Food and Drug Administration (FDA) draft guidance (Submitting Documents Using Real-World Data and Real-World Evidence to FDA for Drugs and Biologics, May 2019);
- International Conference on Harmonisation (ICH) guidelines E3 (Structure and Content of Clinical Study Reports) and E9 (Statistical Principles for Clinical Trials);
- ICH E9(R1) (Addendum: Estimands and Sensitivity Analysis in Clinical Trials, May 2021).

All decisions regarding statistical analysis of the study, as defined in this SAP, will be made prior to database lock for interim analysis or unblinding of the study data for final analysis. The SAP is to be finalized and approved by the sponsor before unblinding of the study data or the lock of study database. Any changes to the final SAP (or SAP amendments, if applicable) after the study database lock will be clarified in the clinical study report (CSR) with “change from the planned analysis”.

The study was terminated early by the Sponsor in Nov 2023. The FDA was notified on 01 Dec 2023, and investigative sites were notified on 04 Dec 2023 to stop enrollment.

Analyses will be performed using SAS® version 9.4 or higher (SAS Institute, Inc., Cary, NC 27513).

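### SAP 6.1 reports crude event percentages over one window that includes the opt-in discontinuation phase, so unequal or informative follow-up could shift the by-arm figures with no drug effect

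*SAP*

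**What the plan says.** SAP 6.1 defines a treatment-emergent serious event as "any serious adverse event that occur after administration of the first dose of study drug and prior to the end of the study". The SAP does not define that end. Protocol 4.4 does: "the date of the last dispensation (last injection of leuprolide; last delivery of relugolix) before the patient transitions to SOC treatment". Protocol 8.3.1 likewise has events "collected from the signing of the ICF until the final study visit", as one continuous period. The window therefore takes in the discontinuation phase.

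The output is introduced by "Tabular summaries with the number and percentage of patients with the following adverse events (but not limited to) will be provided". SAP 6.1 does not repeat the split by arm; that comes from SAP 4.1, which tabulates categorical variables by treatment group. SAP 4.2.1 sets the denominator: everyone randomised who received at least one dose or injection. No table by phase, data cut or patient-year rate is planned, and neither is a count of patients entering the phase.

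Entry to the phase is voluntary. SAP 2.1 lets enrolled patients stay on study drug for up to 12 months, ending Dec 2024, "if they choose to remain in the discontinuation phase of the study". Protocol Appendix 1 adds: "Due to the study entering into a discontinuation phase, all enrolled patients will need to be reconsented". Those who stay keep their randomised drug, and the study is open-label.

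**The concern.** A crude percentage reads as a risk only if the arms are followed for similar times and follow-up does not end for reasons linked to risk. Once a patient can decide, knowing his drug, whether to stay on, neither condition is assured. An arm with more patients in the phase has more time in which to record a first event. If the patients who stay in one arm are healthier than those who stay in the other, its percentage falls.

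The stake is how descriptive tables will be read. Protocol 2.2 says that cardiovascular events will not be adjudicated, so the by-arm SAE tables are where a reader will look for a difference between the drugs. As planned, nothing in them would show whether a difference arose before the stop or afterwards, under selective continuation.

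**Working it through.** **Figures in the plan.** None exists on this point. The documents give no SAE rate, uptake by arm or number actually enrolled. The only design calculation (237 MACE events, SAP 2.2) belongs to the superseded design and does not bear on it. What follows is an illustration on assumed inputs.

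**Model.** Both arms have the same SAE hazard *h* per year. Every patient is followed for *T* years before the cut. A fraction *p* then opts in and is followed for 1 more year; the rest leave but stay in the denominator, as SAP 4.2.1 requires. The percentage with at least one event is

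P = 1 − exp(−hT) × [1 − p + p × exp(−h)]

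**Worked case.** Take h = 0.2 and T = 1, so exp(−0.2) = 0.8187.
- p = 0.9: 1 − 0.8187 × (0.1 + 0.9 × 0.8187) = 31.5%
- p = 0.7: 1 − 0.8187 × (0.3 + 0.7 × 0.8187) = 28.5%
- Ratio 31.5 / 28.5 = 1.10. Up to the cut, both arms stand at 1 − 0.8187 = 18.1%.

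**Range** over h = 0.1, 0.2, 0.3 and T = 0.5, 1:

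| Opt-in, one arm vs the other | Ratio of pooled percentages | Ratio up to the cut |
|---|---|---|
| 80% vs 80% | 1.00 | 1.00 |
| 90% vs 70% | 1.10 to 1.16 | 1.00 |
| 90% vs 50% | 1.22 to 1.39 | 1.00 |

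**Patient-years.** In the worked case the expected time at risk to first event is 0.315 / 0.2 = 1.57 years per patient against 0.285 / 0.2 = 1.43. Events per patient-year are then 0.2 in both arms. A rate therefore removes the artefact when only uptake differs.

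**Informative staying.** Let uptake be 80% in both arms, but let those who stay in one arm have 0.7 times the hazard after the cut. With h = 0.2 and T = 1 the pooled percentages are 26.7% and 30.0%, a ratio of 0.89. Among those who stay, the later rate is 0.14 against 0.20 per year, so a rate does not remove this. A table stopped at the cut does: 18.1% in both arms.

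**Choice of cut.** The SAP dates the stop three ways: "The study was terminated early by the Sponsor in Nov 2023" in section 1, 01 Dec 2023 in 2.1, and 04 Dec 2023 in 2.2 and 3. No planned analysis uses any of them, but a cut needs one. On 04 Dec 2023 sites were told to stop enrolment, and the date is the same for every patient. Re-consent belongs to Amendment 2, dated 29 Feb 2024 (SAP 1), 87 days later, and Protocol Appendix 1 requires ethics approval before an amendment takes effect. The 04 Dec cut therefore precedes any re-consent under it. The periods are not cleanly separate, because patients who had already consented could still be randomised and enter the phase (Protocol 1.1 and 5.3). Anyone first dosed after the cut has no follow-up before it.

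**The case against.** The strongest reply is that no comparison is planned. The objective is to describe the safety of relugolix, Protocol 9.1 rules out formal primary and secondary analyses, and the split by arm is only a general convention. That stands, and it limits the point to how descriptive tables are read.

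It can also be said that the distortion needs a difference between arms that nothing in the documents shows. That stands too: equal uptake and risk give a ratio of 1.00. But the documents do not exclude a difference, and the SAP plans no count of re-consenters by arm that would settle it. The disposition summary in SAP 4.4 could carry one, but its categories are still to be defined. The by-patient SAE listing does not supply it.

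Four stronger readings are tempting, and the documents do not support them.
- *The tables compare self-selected groups.* Patients who decline stay in their arm's denominator (SAP 4.2.1), so selection acts only through length and informativeness of follow-up.
- *After 04 Dec 2023 a patient contributes only if he re-consents.* Re-consent came with Amendment 2, at least 87 days later.
- *Safety follow-up was cut back in the phase.* Protocol 1.3 and 8.2.1 keep the three-monthly questionnaires, which cover SAEs and events leading to discontinuation. The assessments made optional are others.
- *Leaving means a change of class for relugolix patients only, because* "GnRH receptor agonists remain the standard of care for men requiring androgen deprivation therapy (ADT) for advanced prostate cancer" *(Protocol 2.1).* Protocol 6.7 lets patients continue either drug if prescribed, and relugolix is approved. The passage makes arm-dependent choice conceivable, no more.

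**Conclusion.** The point holds as a reporting weakness that is cheap to repair. The SAP gives crude percentages over one window that includes opt-in, open-label follow-up. It offers no cut, no patient-year rate and no count of who continued. The tables remain comparisons of randomised groups; their percentages are distorted only if uptake, time in the phase or the risk of those who stay differs by arm.

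The size depends wholly on assumptions. With identical drugs, 90% against 70% opt-in gives a ratio of about 1.10 to 1.16. The wider 1.22 to 1.39 needs a gap of 90% against 50%.

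A reader might instead model 20% frail patients with three times the event rate of the rest, half of whom leave one arm only. That gives (0.2 × 3 + 0.8) / [(0.1 × 3 + 0.8) / 0.9] = 1.40 / 1.222 = 1.15, with a range of 1.04 to 1.36 for frailty rate ratios of 2 to 4 and 25% to 75% of the frail leaving. That is a rate ratio among those who stay, not the percentage that SAP 6.1 plans, and should not be quoted as the error in the planned tables.

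**What to change.** Keep the pooled tables and add the following to SAP 6.1.
- **(a) Up to the cut.** The AE overview, SAE, fatal SAE and withdrawal tables truncated at 04 Dec 2023, in Safety Population patients first dosed on or before that date.
- **(b) After the cut.** The same tables for later events, including all events in patients first dosed after 04 Dec 2023. Label them as follow-up after the stop and subject to selective continuation. Do not label them non-randomised: patients remain on their randomised drug.
- **(c) Rates.** Patient-years and events per patient-year by arm for each table. These handle unequal time, not selection on risk, so they supplement (a) rather than replace it.
- **(d) Entry counts.** The number and percentage re-consenting to the discontinuation phase, by arm.

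Define the one cut date in the SAP and use it for all these tables.

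The cost is SAP wording and one extra run of existing programs, using data already collected. The downside is smaller counts per table.
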